### **7.5 Expected Risks of Study Related Procedures**

The risks of **venipuncture** are transient pain, bleeding, lightheadedness, bruising, possible vasovagal reaction, and infection. Only trained certified nursing assistants, nurses, nurse practitioners, or physicians will be allowed to perform venipuncture to minimize the risk of complication.

The **DXA and pQCT scans** will expose the subject to ionizing radiation. The level of exposure for this study will be approximately 3.4 millirem which is approximately 1% of that received from natural sources of radiation by a northern US resident in 1 year. Trained staff will perform the scans to minimize the risk of additional exposure. Children unable to sit still through the procedure may be given the option of mild sedation. The minor side effects of sedation include nausea, vomiting, mild allergic reactions, headache and dizziness.

The risks of **completing the questionnaires** may include feelings of sadness due to inability to have an active lifestyle and/or good food intake. Subjects and/or care providers will have the right to refuse to complete any questions that make them uncomfortable. Subjects and/or care providers may also refuse to complete one or more of the questionnaires.

### **7.6 Prohibited Concomitant Therapy**

Prior and/or concomitant medical therapy with other bisphosphonates, Denosumab, or Teriparatide will not be permitted during the study.

Treatment with an investigational agent will also be prohibited within the 4 weeks prior to randomization (Day 90) and for the duration of the study (Day 90 through Day 360).

All other therapies are permitted.

### **7.7 Duration of Study Therapy**

Refer to section 7.3.6 for regarding criteria for early discontinuation of pamidronate.

All subjects will receive calcium and vitamin D supplementation per protocol through the Day 360 post-HCT visit unless one of the following occurs:

- Subject voluntarily withdraws or their parent(s)/legal guardian(s) voluntarily withdraws them from the study
- Subject is not eligible for randomization at the Day 90 visit
- Subject requires treatment with a prohibited medical therapy per section 7.5
- Pregnancy
- Non-compliance
- Subject's well-being, in the opinion of the Investigator, would be compromised by continuation of pamidronate administration
- Disease relapse occurs and post-HCT follow-up ends
- The study ends early

Note: if a participant assigned to the Control Arm experiences a clinically significant fracture after Day 90, if medically appropriate, pamidronate treatment may be started (independent of the study and not covered by research funds). The participant could remain on study with analysis within the original study assignment (control).

Subjects discontinued from the study therapy but are considered evaluable for analysis (i.e. has been randomized and, if applicable has received at least 1 dose of pamidronate) will continue study participation per section 8 unless consent is withdrawn.

If a subject withdraws after an adverse event (AE), they will be followed until resolution of the issue or until their condition is stable.

In the event that a subject becomes pregnant, discontinuation, reporting, and follow-up procedures outlined in Section 9.3 will be followed.

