Correlative Objectives:	
 
• Cytokine levels will increase rapidly in the first 3 weeks after HCT, preceding an increase in markers of bone resorption.
 
• In the Control Group, increased cytokine levels and receptor activator of nuclear factor-<math>\kappa</math> B ligand (RANKL)/osteoprogenin (OPG) ratio 3 weeks post-HCT will be associated with decreased BMC and BMD at 1 year post HCT.
 
• Markers of bone resorption will increase in the first three months after HCT, will remain elevated until at least Day 180 in the Control Group, but will decrease after initiation of pamidronate at Day 90 in the Pamidronate Group.
 
• Markers of bone formation, including osteocalcin (OCN) will decrease in the first three months after HCT and in the Control Group lower OCN levels at Day 90 will be associated with lower BMC and BMD 1 year post-HCT.
 

Duration of Study Participation	1 year from HCT
Number of Subjects	60 evaluable patients (30 per site) over 3.5 years

Main Inclusion Criteria	Subjects will be $\geq 1$ and $\leq 20$ years of age at the time of enrollment and receiving an allogeneic HCT for a hematologic malignancy in complete remission and using a myeloablative preparative regimen, non-malignant diseases with a myeloablative or non-myeloablative preparative regimen, or severe aplastic anemia (SAA) for which any conditioning therapy is permitted.
Standard Therapy	All Subjects - Standard supplementation with calcium and vitamin D beginning at admission to the hospital (prior to HCT) and continuing until post-HCT Day 360 visit
Study Product, Dose, Route, Regimen	Pamidronate Group Only Pamidronate disodium single 1 mg/kg intravenous infusion administered every 3 months for 3 doses - post-HCT Days 90, 180 and 270.
Endpoints	The primary study endpoint is lumbar bone mineral content (LBMC).  Other endpoints are TBMC (excluding head), bone strength, total BMD, cortical BMD, trabecular BMD, levels of markers of bone turnover, cytokines, RANKL/OPG ratio, and body composition.
Statistical Methods	The primary analysis will compare the Pamidronate and Control Groups according to LBMC measured by DXA using a t-test applied to all available Day 360 measurements. A secondary analysis will use multiple imputation to impute Day 360 BMC and BMD measurements for each subject who does not provide one.

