#### Treatment Plan:

##### All subjects:

**Vitamin D and Calcium Supplementation** per Section 7.3 begin prior to HCT preparative regimen start (e.g. on day of admission for transplant) and continue daily through day 360 post-HCT milestone visit

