#### **7.4.2 Treatment Plan Modification for Elevated Serum Creatinine**

If at the time of a planned pamidronate infusion, the patient's serum creatinine level is  $>2$  times that of the baseline level (done at Study Enrollment or Study Entry), pamidronate will be held.

If the creatinine level decreases to  $\leq 2$  times the baseline level within 2 weeks, the pamidronate may be given as planned.

If it remains elevated for more than 2 weeks, the subject will skip the scheduled dose of pamidronate. If at the time of the next pamidronate dose (if applicable) the subject's creatinine level has not returned to  $<2$  times that of the baseline value pamidronate will be permanently discontinued, but the subject will continue vitamin D and calcium supplementation.

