#### **7.4.6 Criteria for Discontinuation**

Subjects receiving pamidronate will discontinue pamidronate if any of the following conditions exist:

- Clinically significant allergic reaction (tongue or facial swelling or wheezing) to pamidronate
- Subsequently meets any of the study exclusion criteria (section 5.2) except for clinically significant current fracture, in which case pamidronate will be continued
- If creatinine level increases to > 2 times baseline level and a dose of pamidronate must be skipped for a 2nd time per section 7.3.2.
- Unacceptable toxicity (e.g. osteonecrosis of the jaw)
- Positive pregnancy test - Refer to section 9.3 regarding the reporting of pregnancy during study treatment.
- Disease relapse
- Subject's well-being, in the opinion of the Investigator, would be compromised by continuation of pamidronate administration.

These subjects will continue to be enrolled in the study, receiving vitamin D/calcium and participating in study procedures as planned unless contraindicated. An exception to this plan is for those patients who have a worsening of their disease (relapse) and discontinue routine post-HCT follow-up at the enrolling institution. In this situation, patients would be taken off study with no further study procedures.

Subjects who discontinue pamidronate treatment after the first dose (Day 90) will be included in the statistical analyses as members of the Pamidronate Group under the principle of intention-to-treat.

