c Including Tanner staging of pubertal development.

d Females >10 years only.

e If documentation of a negative pregnancy test within 7 days prior to DXA scan is available, the pregnancy test does not need to be repeated.

f If result is below the lower limit of normal refer to section 7.2 and 7.3.

g Subjects who have vitamin D levels ( $D_2+D_3$ ) <20 ng/ml at Day 90 will not be eligible for randomization per section 6.2.

h L1-L4 and total body scans with body composition.

i Subjects at the University of Minnesota (UMN) only.

j All subjects will begin taking supplemental vitamin D per day and calcium, if needed, to meet recommended dietary allowance (RDA) requirement upon admission to the hospital for the HCT and continue through Day 360. If a subject has low vitamin D ( $D_2+D_3$ ), dietary calcium intake is below RDA, or the ionized/or corrected calcium level is below the normal range, additional vitamin D and/or calcium supplementation will be given per Section 7.3.

k For subjects randomized to the Pamidronate Group, 1 mg/kg (60 mg max) will be administered via intravenous (IV) infusion over 4 hours. Subjects will be given 15 mg/kg acetaminophen (or maximum of 500 mg) prior to infusion then every 4 hours as needed for a maximum of 24 hours. Postmenarchal subjects randomized to pamidronate will be put on an oral contraceptive pill (Loestrin or Orthocept or other OCP that contains 30 mcg ethinyl estradiol), birth control patch or other effective method of birth control. The results of the serum creatinine and pregnancy test (if applicable) must be reviewed before drug administration.

l Pamidronate patients only

m Serum creatinine level and spot urine collected the morning after each pamidronate infusion; however if not feasible at that time may be done anytime within 7 days after pamidronate infusion. A morning collection is preferred, but not mandatory. The time of the urine collection must be recorded.

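### Section 7.7 makes harm from continued pamidronate a reason to end calcium and vitamin D, while Section 7.4.6 stops only pamidronate on the same ground

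*Combined protocol and SAP*

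**What the plan says.** Section 7.7 opens by sending the reader elsewhere, to Section 7.3.6, for "criteria for early discontinuation of pamidronate". It then sets its own rule for the supplements: "All subjects will receive calcium and vitamin D supplementation per protocol through the Day 360 post-HCT visit unless one of the following occurs". One of the events listed under that rule is "Subject's well-being, in the opinion of the Investigator, would be compromised by continuation of pamidronate administration".

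Section 7.4.6 lists the reasons to discontinue pamidronate. Its last item is the same sentence, identical apart from a final full stop. The consequence is different: "These subjects will continue to be enrolled in the study, receiving vitamin D/calcium and participating in study procedures as planned unless contraindicated". The only exception named there is relapse with the end of routine follow-up at the enrolling institution.

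Section 7.4.2 deals with creatinine that stays elevated and reaches the same result as 7.4.6: "pamidronate will be permanently discontinued, but the subject will continue vitamin D and calcium supplementation".

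Three general statements run the supplements to the end of the study:
- the synopsis: "Standard supplementation with calcium and vitamin D beginning at admission to the hospital (prior to HCT) and continuing until post-HCT Day 360 visit";
- the schema, where all subjects "continue daily through day 360 post-HCT milestone visit";
- Section 8.1, note j, where all subjects begin supplements "upon admission to the hospital for the HCT and continue through Day 360".

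**The concern.** One trigger leads to two instructions. If an investigator decides that further pamidronate would harm a child, 7.4.6 stops the drug and keeps the supplements, while 7.7 treats the same decision as ending per-protocol supplements. A coordinator asking how long the supplements run would look first in 7.7, because its title concerns the duration of study therapy. The pointer there to the pamidronate rule carries a number that no longer exists, so it does not lead to 7.4.6.

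Two things are at stake. First, the trial compares pamidronate plus supplements with supplements alone, so the background should be the same in both arms. The condition concerns continuing pamidronate, so it can hardly be met in the control arm. The one route is a control child started on pamidronate outside the study after a fracture, which 7.7 allows. Second, Section 1.2 says that calcium and vitamin D prevent or mitigate the transient hypocalcemia seen with the drug. Taken at its word, the bullet would lift routine supplements from children who have already received it.

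**Working it through.** No arithmetic beyond a count applies. The check sets the sections side by side.

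**Step 1: what the 7.7 list governs.** Its eight events are voluntary withdrawal, ineligibility for randomization at Day 90, need for a prohibited therapy, pregnancy, non-compliance, the well-being condition, relapse with follow-up ended, and early end of the study. Stopping rules for pamidronate are sent to another section before the list begins, so the list governs the supplements. Of the eight, one names pamidronate (1 of 8).

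**Step 2: what each section does when pamidronate stops.**

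| Place | Trigger or scope | Calcium and vitamin D |
|---|---|---|
| 7.7 | Investigator judges continued pamidronate harmful | Per-protocol course ends |
| 7.4.6 | Same sentence | Continue unless contraindicated |
| 7.4.2 | Creatinine still elevated at the next planned dose | Continue |
| Synopsis | All subjects | To Day 360 |
| Schema | All subjects | To Day 360 |
| 8.1, note j | All subjects | To Day 360 |

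The 7.7 bullet stands against five other places, two of them specific to children who have stopped the drug.

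**Step 3: can the two lists be reconciled?** The qualifier in 7.4.6 about contraindication does not do it. The trigger is harm from pamidronate, and that by itself is no contraindication to calcium or vitamin D. The relapse items need no reconciling, since 7.4.6 and 7.7 both tie the end of participation or supplements to the end of post-transplant follow-up.

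**Step 4: what would lapse on the literal reading.** Under 7.3.1, a child with sufficient vitamin D, normal calcium and adequate diet receives 600 IU of vitamin D a day and no calcium. With low dietary intake the calcium top-up is 600, 1,000 or 1,200 mg a day, depending on age. These routine amounts are what the bullet would mainly remove.

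**Step 5: what remains in force.**
- 7.1 requires added vitamin D for a level below 30 ng/mL at the designated time points through Day 360.
- 7.2 requires calcium and vitamin D under 7.3 if a level is below the normal range at any time, and note f of 8.1 sends a low calcium result to the same place.
- 7.6 permits all therapies other than those it prohibits, so clinicians may supplement outside the protocol.
- 7.7 itself keeps evaluable subjects who come off study therapy in the Section 8 procedures unless consent is withdrawn.
- 7.4.6 and 12.2 keep them in the analysis as randomized.

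**The case against.** The strongest reply is that the rest of the protocol already settles the matter. Section 7.4.6 deals with exactly these children and says what happens to them, 7.4.2 agrees, and three general statements run the supplements to Day 360. On that view the 7.7 bullet is a sentence copied into the wrong list, and staff would see as much. Most of this stands: it does look like a drafting slip. But the slip sits in the section that defines duration of therapy, and the pointer that should lead to the clear rule is out of date, so it deserves correction.

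A second reply is that 7.7 only lifts a requirement and orders no stop. That reading is possible. Against it, the same section goes on to speak of subjects discontinued from study therapy, which makes the list work as stopping criteria. Even on the softer reading, 7.4.6 requires supplements where 7.7 does not.

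A third reply is that little harm follows. This stands. Deficient children are still treated under 7.1 and 7.2, Section 1.2 calls the hypocalcemia transient, and the trigger itself means no further infusions.

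A reader might go further and infer that the plan deliberately withdraws supplements from one arm, that hypocalcemia would go untreated, or that the Day 360 comparison of lumbar bone mineral content is biased or loses power. The documents support none of these. The other sections show the contrary intent, low levels are still treated, follow-up and the intention-to-treat analysis are kept, and no rate of such stops is given from which an effect could be worked out.

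**Conclusion.** The inconsistency is real: for one and the same trigger, 7.7 ends per-protocol calcium and vitamin D and 7.4.6 continues them unless contraindicated. Section 7.7 is the outlier. It is a minor fault in an operative rule. On the literal reading it would remove routine supplementation almost only from pamidronate-exposed children, and what would lapse is mainly maintenance vitamin D and dietary calcium top-up.

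This rests on two readings: that the 7.7 list consists of stopping criteria for the supplements, and that 7.1 and 7.2 continue to apply to a child who has met one of them. No numerical effect on the arms, on power or on the primary endpoint can be stated, because the documents do not say how often investigators would stop pamidronate on this ground.

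**What to change.** In the 7.7 bullet, replace the reference to pamidronate administration with calcium/vitamin D supplementation. The pamidronate trigger then appears only in 7.4.6, where its consequence is spelled out. Rewording is preferable to deleting the bullet, because it keeps an investigator-judgement stop for the supplements themselves.

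In the opening line of 7.7, correct the pointer from 7.3.6 to 7.4.6. Section 7.3 now holds the supplementation charts and ends at 7.3.4.

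The cost is two wording changes in one section at the next amendment. Visits, tests, sample size and analysis stay as they are.

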### **6.2 Randomization (Day 90 Post-HCT Visit +/- 14 days)**

Randomization to pamidronate (Pamidronate Group) or no pamidronate (Control Group) will occur at Day 90 (+/- 14 days) by the institutional study coordinator based on the randomization schedule developed by the study statistician and entered into OnCore.

A brief review of continuing eligibility will be done and subjects will not be eligible for randomization if one or more of the following are true:

- Vitamin D ( $D_2+D_3$ )  $<20$  ng/ml as use of pamidronate is contraindicated due to potentially higher risk of hypocalcemia. Levels should be measured within 14 days prior to randomization.\*\*†
- serum creatinine is  $> 2$  times the baseline value (at Study Entry) - perform within 14 days prior to randomization
- an investigational study drug or agent, including biphosphonates, Denosumab, or Teriparatide, was administered within the previous 4 weeks or is planned for use during study participation (Day 90 through Day 360)
- positive pregnancy test (performed within 14 days prior to randomization)
- Inability to successfully complete a DEXA scan
- the parent or adult patient refuse randomization
- disease relapse has occurred

The randomization will be stratified by age with 2 strata:  $< 10$  years old and  $\geq 10$  years old.

If the patient is ineligible for or refuses randomization, no further research related procedures or treatment will occur after the Day 90 visit; however permission to continue review of the patient's medical record through the Day 360 visit for routine clinical information is embedded within the consent form document. This information will be collected only if the patient continues care at the enrolling

institution. Patient care will be at the discretion of the treating physician(s) and independent of this study.

OnCore will automatically generate an email alerting key study personnel of the randomization (or lack of).

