**7.4 Pamidronate**

**7.4.1 Treatment Plan**

Subjects randomized to the Pamidronate Group will receive 3 single doses of pamidronate at 3-month intervals (Day 90 +/-14 days, Day 180 +/-14 days, and Day 270 +/-30 days).

Note: All time point specific laboratory testing procedures (sections 8.1 and 8.3) must be collected prior to the pamidronate infusion (except those specifically designated post infusion); however for ease of scheduling the consultations as well as the Day 90 DXA and Day 90 pQCT may be performed after the infusion as long as done within the +/-14 day window. Ionized calcium or corrected calcium, and Vitamin D levels (D2+D3) will be drawn prior to pamidronate infusions. If either are low, the subject should receive supplemental calcium and/or Vitamin D per Section 7.3. If the subject is receiving supplemental calcium, an ionized or corrected calcium level should be drawn after the pamidronate infusion end but prior to discharge from clinic on the day of the pamidronate.

Prior to each infusion the patient will be assessed and pamidronate will be held if:

- Serum creatinine is > 2 times the baseline (Study Entry) level – refer to section 7.3.2 for monitoring plan – the pre-treatment creatinine may be done anytime within 72 hours prior to the planned pamidronate administration

- Pregnancy test is positive (subject will permanently discontinue study drug) per section 7.3.5 – pregnancy testing may be done anytime within 72 hours prior to the planned pamidronate administration

Pamidronate 1 mg/kg (to a max dose of 60 mg) will be administered via a single IV infusion over 4 hours using a line separate from all other drugs. Dosing will be based on the patient's actual weight or, if overweight, on ideal body weight (IBW). This will be followed by a normal saline flush of 20 cc total given at the same rate as the pamidronate.

Premedication: Subjects will be given 15 mg/kg acetaminophen (or maximum of 500 mg) prior to pamidronate infusion then every 4 hours as needed for a maximum of 24 hours.

Post-Pamidronate Infusion Laboratory Tests: A serum calcium level will be done after the pamidronate infusion end but prior to discharge from clinic on the day of the pamidronate.

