## **12 Statistical Considerations**

### **12.1 Sample Size**

Sixty (60) subjects total (30 each in the Control and Pamidronate groups) gives 80% power to detect a difference between groups of 0.75 standard deviations (SDs)

describing variation in LBMC within study group after adjusting for height, age, sex, Tanner score, and race. Adjusting for age and sex, this SD is 5-8g (46, 47); adjusting further for race and height should reduce this SD by about half (48-50). This gives a within-group SD of about 2.5-4g and a detectable difference of 2-3g. To have 60 evaluable subjects, 192 need to be screened to allow for a 50% consent rate, 10% death rate by Day 90, 20% death rate between Day 90 and Day 360, and 10% drop out after randomization.

Anticipated Enrollment Over Duration of Study

	Screen	Study Entry Day -14 a	Day 7	Day 14	Day 21	Day 90	Day 180	Day 270	Day 360
Total	192	96	96	96	96	86	86	86	60
University of Minnesota (UMN)	96	48	48	48	48	43	43	43	30
Fred Hutchinson Cancer Research Center	96	48	48	48	48	43	43	43	30
a Day 0 is the day of hematopoietic cell transplantation (HCT).									

According to data from 2011 to 2012, 36 allogeneic transplants have been performed at UMN and 37 have been performed at Fred Hutchinson Cancer Research Center. It is expected that screening 28 patients per year will be feasible for both sites.

It anticipated that enrollment will take 3.5 years.

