## 12.2 Subject Population(s) for Analysis

All randomized subjects will be included in the primary analysis according to their randomized treatment assignment, consistent with the principle of intention-to-treat.

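### Section 7.7 makes a first pamidronate dose a condition of being evaluable and staying in follow-up, which can bind in one arm only and contradicts the intention-to-treat set in 12.2

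*Combined protocol and SAP*

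**What the plan says.** Section 7.7 deals with children who have come off study therapy. Those "considered evaluable for analysis (i.e. has been randomized and, if applicable has received at least 1 dose of pamidronate) will continue study participation" under section 8, which includes the Day 360 DXA, unless consent is withdrawn. This is the only place where the plan defines evaluable, the term in which the target of 60 is set.

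Section 12.2 sets a different population: "All randomized subjects will be included in the primary analysis according to their randomized treatment assignment". It has no dosing condition. Section 7.8 ends participation at Day 360, or earlier for withdrawal or for relapse with the end of post-transplant follow-up. It does not mention dosing either.

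Section 7.4.6 adds that "Subjects who discontinue pamidronate treatment after the first dose (Day 90) will be included in the statistical analyses" as members of the Pamidronate Group. It does not say what happens to a child assigned to pamidronate who never receives a dose.

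Section 12.4 runs the primary regression on the lumbar BMC measurements available at Day 360.

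**The concern.** A control meets the 7.7 definition by being randomised. A child assigned to pamidronate must also have been infused at least once. The extra condition depends on something that happens after randomisation, in an open-label trial, and it has no counterpart among controls.

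The plan leaves room for such children. If a coordinator reads 7.7 literally and ends their section 8 procedures, they have no Day 360 scan and drop out of the primary analysis. The pamidronate arm becomes a dosed-only group while the control arm remains as randomised. Section 12.2 would then claim an intention-to-treat comparison that the data could not deliver, and a scan not taken at Day 360 cannot be recovered. The imputation of Day 360 BMC in the synopsis is labelled secondary, and section 12.4 applies imputation only to Aims 2 and 3 and Aim 1 Hypothesis 2.

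**Working it through.** **1. The plan's own figures.** Section 12.1 states "subjects total (30 each in the Control and Pamidronate groups") and that this "gives 80% power to detect a difference between groups of 0.75" SD.

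- Accrual: 192 × 0.50 = 96; 96 × 0.90 = 86.4 (stated 86); 86 / 2 = 43 per arm at Day 90. With additive losses, 86 × (1 − 0.20 − 0.10) = 60.2 (stated 60).
- Power: alpha and sidedness are not stated. Assuming 0.05 two-sided, a two-sample t-test needs 28.9 per arm and has power 0.815 at 30 per arm.
- Scale: "This gives a within-group SD of about 2.5-4g and a detectable difference of 2-3g"; 0.75 × 2.5 = 1.9 g and 0.75 × 4 = 3.0 g.

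The figures reproduce. None of the allowances (consent, death, drop-out) is for children randomised but not dosed.

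**2. The sections side by side, for a randomised child with no pamidronate dose who is off study therapy.**

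| Section | Assigned to control | Assigned to pamidronate |
|---|---|---|
| 7.7 | evaluable, continues | does not meet the definition |
| 7.8 | participates to Day 360 | participates to Day 360 |
| 7.4.6 | not applicable | inclusion confirmed only after a first dose |
| 12.2 | analysed as assigned | analysed as assigned |

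**3. Can such a child arise?** Yes, by at least three routes.

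- The trial is open-label, so a family may decline infusion after learning the assignment.
- Section 6.2 accepts a creatinine result up to 14 days old at randomisation, while 7.4.1 asks for one within 72 hours of infusion. The threshold is the same (more than 2 times baseline); only the window differs. Under 7.4.2 a persistently raised value means that the dose is skipped, and a value still raised at the next dose ends pamidronate. A child who fails at both Day 90 and Day 180 has had none. Section 7.4.2 then continues supplements and does not mention study procedures.
- Section 7.4.6 stops pamidronate for any section 5.2 criterion except fracture. Section 6.2 does not re-check all of these, for example an impending dental procedure (5.2.11) or creatinine above the age limit (5.2.4). As an illustration with the UMN upper limit of 0.53 mg/dL for 22 days to 8 years: a baseline of 0.30 and a Day 90 value of 0.55 give a ratio of 1.83. That passes 6.2 yet meets 5.2.4.

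**4. Size.** The documents give no undosed rate. Assume k = 1 to 6 of 43, so u = k/43. Dropping these children moves the pamidronate mean by u × d, where d is the difference in adjusted LBMC between dosed and undosed children, assumed to be 0.5 to 1 SD. If they are kept and have no treatment effect, the expected difference is 0.75 × (1 − u). Power below uses the normal approximation, two-sided 0.05; it is 0.828 at k = 0.

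| k | u | Shift if dropped (SD) | Pamidronate n if dropped, 30(1 − u) | Power if dropped | Effect if kept (SD) | Power if kept |
|---|---|---|---|---|---|---|
| 1 | 0.023 | 0.012–0.023 | 29.3 | 0.823 | 0.733 | 0.810 |
| 4 | 0.093 | 0.047–0.093 | 27.2 | 0.809 | 0.680 | 0.750 |
| 6 | 0.140 | 0.070–0.140 | 25.8 | 0.798 | 0.645 | 0.705 |

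The shift runs from 0.012 × 2.5 = 0.03 g to 0.140 × 4 = 0.56 g. As a share of the target difference that is 0.012/0.75 = 2% to 0.140/0.75 = 19%. Dropping the children costs at most 0.828 − 0.798 = 0.03 in nominal power. The issue is therefore one-sided exclusion, not sample size.

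**The case against.** The strongest reply is that nothing in the plan expels an undosed child. Section 7.7 says who continues and does not say that others stop. Section 7.8 governs participation and has no dose condition. Section 7.4.6 keeps children who stop pamidronate enrolled and in study procedures, and it never uses the term evaluable. Section 12.2 defines the analysis set and names everyone randomised. Randomisation and first infusion belong to the same Day 90 visit, so the gap between them should be short. Under 7.4.2 a child who skips Day 90 may still be dosed at Day 180, and then meets even the 7.7 wording.

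Most of this stands, and it limits how far the point goes. A reader might infer that undosed children are definitely removed and that the intention-to-treat set is lost. The documents do not support that: the set is contradicted and put at risk.

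A reader might also take pregnancy as an example, since 6.2 lists a "positive pregnancy test (performed within 14 days prior to randomization") while in 7.4.1 "pregnancy testing may be done anytime within 72 hours prior to the planned pamidronate administration". It is not a one-arm exit, because section 9.3 withdraws a pregnant subject from either arm.

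The reply does not remove the conflict. The retention sentence in 7.4.6 refers to subjects receiving pamidronate and does not clearly reach a child never infused. Section 7.8 disagrees with 7.7 and does not settle which one governs.

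**Conclusion.** The point holds as an internal contradiction in the follow-up and analysis population. Section 7.7 is wrong as written: its dose condition can apply to one arm only, and it conflicts with 12.2 and 7.8. Section 7.4.6 leaves the same gap.

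The number affected is unknown and probably small. Under the assumed 1 to 6 undosed children of about 43 and a difference of 0.5 to 1 SD, literal use of 7.7 would move the pamidronate mean by about 0.01 to 0.14 SD against the 0.75 SD target. Both ranges are assumptions. A reader might infer that the bias favours pamidronate, but the documents do not say whether undosed children would have lower or higher bone mass than their arm-mates, so the direction is open. The contradiction itself does not depend on these figures.

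**What to change.** - **Section 7.7:** delete the first-dose condition. State that every randomised child, dosed or not, continues section 8 procedures including the Day 360 DXA and is analysed as assigned. The only exceptions should be exits that apply equally to both arms: withdrawal of consent, relapse with the end of follow-up (7.8), and withdrawal under 9.3.
- **Section 7.4.6:** make the intention-to-treat sentence match, so that it also covers children assigned to pamidronate who never receive a dose.
- **Reporting:** give the number randomised but undosed, by arm.
- **Separately:** ask the sponsor to reconcile the eligibility criteria and test windows in 5.2, 6.2, 7.4.1, 7.4.2 and 7.4.6. Which clinical rule should apply is for the sponsor to decide.

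The cost is wording in two sections and a few extra Day 360 visits. Keeping undosed children may dilute the estimated effect. In the assumed range, nominal power would fall from 0.828 to between 0.810 and 0.705 if those children had no benefit. That is the price of the comparison that 12.2 already promises.
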